## **1. INTRODUCTION**

### **1.1. BACKGROUND**

Total knee arthroplasty (TKA) and total hip arthroplasty (THA) have evolved into immensely successful procedures for the treatment of a variety of knee and hip joint pathologies. However, due to a number of indications, including infection, mechanical loosening, instability, polyethylene wear, stiffness, and periprosthetic fracture there remains a growing need for revision TKA and revision THA. Revision total joint surgery is a large financial burden to the United States healthcare system with projections assuming over a 5-fold increase by 2030^4. Advancements in postoperative care, surgical planning, patient selection and surgical technique have improved revision TJA outcomes. However, an often-overlooked variable in revision total joints is an effective wound closure. Effective wound closure is essential in the immediate and long-term outcomes of post-operative complications, wound healing, operative efficiency, and patient satisfaction after primary or revision total joint arthroplasty.

Revision TJA is usually performed through non-naïve tissue planes creating concerns for wound healing and tissue vascularity. Incisions are typically larger than primary joint arthroplasties, may take longer to close and involve more complex closures. Decreasing closure time is appealing as not only is it cost effective but there is data to support increased operative time increases risk for infection.

Barbed suture has been studied in primary hip and knee arthroplasty with data demonstrating faster closure times, cost efficiency, and no increase in glove perforation. Cadaveric studies indicate barbed suture creates a more water tight arthrotomy closure, which can reduce wound drainage. Prolonged wound drainage and hematoma formation increase the risk for surgical site infection and deep wound infection. Biomechanical studies under cyclic loading barbed suture is equivalent to conventional interrupted closure and performed better when intentionally damaged and cycled which clinically may translate to decreased wound dehiscence. Wound dehiscence is a risk factor for recurrence of infection after two stage reimplantation

In the setting of revision for infection monofilament and antibacterial sutures are used to decrease bacterial adherence and load in the surgical wound. In primary total joint arthroplasty braided antibacterial absorbable suture and barbed suture have been shown to be as efficacious, with barbed suture having faster closure times and overall cost savings. Monofilament barbed suture has outperformed braided suture in contaminated wound models and performed equally well as monofilament suture.

Our institution does a large number of revision arthroplasties, closure is determined by surgeon preference, with variability amongst surgeons. Retrospective review performed by Levine et al report no notable adverse response to barbed suture in primary or revision arthroplasty and no change in complication or wound healing rates since adopting barbed suture closure with decreased closure time. To our knowledge there has been no prospective randomized studies performed on barbed suture in the revision setting.

### **1.2. RATIONALE**

Our study seeks to demonstrate efficacy of barbed suture closure in the revision setting. Use of barbed suture has been demonstrated to be safe in primary hip and knee surgery however no one has prospectively investigated barbed suture closure in the revision setting (9,14,16-18). Animal and biomechanical studies have shown that barbed suture is equivalent to monofilament in revision setting for infection and outperforms traditional suture for strength in arthrotomy closure. By comparing traditional closure with barbed suture, we can decrease wound closure time, control costs, and number of needles handled by operative staff without sacrificing cosmesis.

There have been no prospective randomized trials of barbed vs traditional suture in the revision setting. In a single center retrospective review Levine et al found no notable differences in wound healing or complications for primary and revision total joints treated with barbed suture closure as compared to their historic rates (9).

## **2. STUDY OBJECTIVES AND HYPOTHESIS**

### **2.1. PRIMARY STUDY OBJECTIVE**

Barbed suture has been demonstrated to be safe in primary hip and knee surgery and retrospective data suggests barbed suture represents no increased complications in the revision setting. Barbed suture may represent a faster, more effective way to perform revision arthroplasty closures. There are no Level I studies comparing traditional and barbed suture closure. The purpose of this study is to assess the surgical complexities of closures using closure time without sacrificing cosmesis or wound complications between the traditional closure and barbed closure.

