#### *Secondary Objectives*

1. To evaluate the cost effectiveness of using bidirectional barbed suture compared with traditional sutures in revision knee and hip arthroplasty
2. To evaluate prevalence of complications (including needle sticks and glove perforations) of using barbed suture in revision total joint arthroplasty
3. To evaluate the cosmetic result of barbed versus traditional suture in revision total joint arthroplasty
4. To quantify the number of sutures used for each type of closure
5. To perform cost analysis to determine most cost-effective closure

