#### *Secondary Endpoints*

1. Record all complications (including needle sticks and glove perforations) and infections related to the wound closure
2. Calculate the cost difference based on supplies, personnel, and OR time between each technique
3. Gather pictures of wound following closure to evaluate the cosmetic result of barbed versus traditional suture in revision total joint arthroplasty using the Patient and Observer Scar Assessment Scale (POSAS)
4. Calculate the number of suture used and length of incision for each technique

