### Statistical Analysis

Descriptive statistics will be used to report baseline characteristics as well as primary and secondary outcomes for the barbed suture and conventional cohorts. Outcomes will be compared between barbed suture and conventional closure (control) for the aforementioned baseline, perioperative and postoperative variables. Continuous or ordinal variables will be reported using unpaired t-tests, and all other categorical variables will be analyzed using Fisher's Exact Test. The test for primary endpoint will be one-sided (with the alternative hypothesis "mean closure time for barbed suture minus mean closure time for traditional suture <0") with a significance level of 0.025. Two-sided tests will be performed for baseline characteristics of patients and secondary endpoints with a significance level of 0.05. To further control for surgeon and evaluator variability we will also perform multivariable linear regression for continuous outcomes of interest and logistic regression for the dichotomous outcomes. Pooled and subgroup analysis for hip and knee revisions will be performed

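### The stated purpose is faster closure with no loss on cosmesis or wound complications, but the planned analysis cannot support a no-worse statement; separately, the complication window is inconsistent

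*Combined protocol and SAP*

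**What the plan says.** All references are to the combined protocol and SAP.

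- **Purpose.** Section 2.1 describes assessing closures "using closure time without sacrificing cosmesis or wound complications between the traditional closure and barbed closure". Section 1.2 expects barbed suture to shorten closure and "control costs, and number of needles handled by operative staff without sacrificing cosmesis".
- **Listed objectives and endpoints.** These are more modest. The secondary objective is "To evaluate prevalence of complications (including needle sticks and glove perforations) of using barbed suture in revision total joint arthroplasty" and the matching endpoint is "Record all complications (including needle sticks and glove perforations) and infections related to the wound closure". Cosmesis is likewise to be evaluated, using POSAS.
- **Analysis (section 12).** Descriptive statistics are planned for primary and secondary outcomes. For testing, "Continuous or ordinal variables will be reported using unpaired t-tests" and "all other categorical variables will be analyzed using Fisher's Exact Test". The level is set by: "Two-sided tests will be performed for baseline characteristics of patients and secondary endpoints with a significance level of 0.05". Adjustment for surgeon and evaluator uses linear regression and "logistic regression for the dichotomous outcomes". Pooled and by-joint analyses are planned.
- **Sample size (section 12).** The trial is sized for closure time and for cost only.
- **Complication window.** Section 9.e.ii assesses complications at standard-of-care visits up to six months. The schedule in section 9.f shows follow-up over 0-90 days. Section 10 ends each participant's data collection at the 90-day visit.

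**The concern.** Sections 1.2 and 2.1 use no-worse language, whereas section 12 looks only for a difference. Failing to find a difference is not evidence that none exists, and a no-worse statement needs a bound on how much worse barbed suture could be. Nothing in the plan supplies that bound. The only numerical safety limits, in section 15, are triggers within a group for suspending the study, not a comparison between arms.

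At stake is what the trial may conclude. A faster closure with p > 0.05 for complications and POSAS could be reported as achieving the stated purpose, although the data might be compatible with a material excess of wound problems.

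The window is a separate matter. A deep infection or re-revision on day 120 would fall inside one section's follow-up and outside the other two.

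**Working it through.** **1. The plan's own figure.** Inputs from section 12: difference 5 minutes, SD 5 minutes, one-sided alpha 0.025, power 80%.

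- Normal approximation: n = 2(1.960 + 0.842)² × (5/5)² = 15.7, so 16 per group.
- The t-test (noncentral t) gives 16.7, so 17 per group, with power 80.7%. The stated 17 reproduces.
- Allowing for 15% loss: 34/0.85 = 40 per joint, 80 in total. That also reproduces.

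With equal arms this means 20 per arm within a joint and 40 per arm pooled. After 15% loss it is 0.85 × 20 = 17 and 0.85 × 40 = 34.

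**2. Power of the planned Fisher test to detect a doubling.** The documents give no complication rate, so the rates below are assumptions. Power is the sum, over all pairs of counts (i, j), of Bin(i; n, p₁) × Bin(j; n, p₂) where the two-sided Fisher p is at most 0.05.

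| Control v barbed | 40 per arm | 34 per arm | 20 per arm | 17 per arm |
|---|---|---|---|---|
| 5 v 10% | 4% | 3% | 2% | 1% |
| 10 v 20% | 16% | 12% | 7% | 5% |
| 20 v 40% | 41% | 34% | 19% | 14% |
| 25 v 50% | 56% | 49% | – | – |
| 30 v 60% | 73% | 62% | – | – |

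So in the pooled comparison a doubling would more likely than not be missed at control rates up to about 20%, but not once the rate reaches about 25-30%.

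**3. What an interval would show.** Newcombe 95% interval for d = p₁ − p₂, where (l, u) are each arm's Wilson limits:

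- lower = d − √[(p₁ − l₁)² + (u₂ − p₂)²]
- upper = d + √[(u₁ − p₁)² + (p₂ − l₂)²]

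Example, 8/40 barbed v 4/40 traditional. The Wilson limits are 0.105 to 0.348 and 0.040 to 0.231.

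- lower = 0.100 − √(0.095² + 0.131²) = −0.061
- upper = 0.100 + √(0.148² + 0.060²) = +0.259
- Fisher p = 0.35

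The test is non-significant, yet the data are compatible with anything from 6 points better to 26 points worse.

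Equal observed counts give these half-widths:

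| Counts in each arm | Half-width (points) |
|---|---|
| 2/40, 4/40, 8/40 | 12.1, 14.4, 17.6 |
| 2/34, 3/34, 7/34 | 13.9, 15.3, 19.2 |

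The logical gap remains when events are common. With 20/40 v 16/40 (a ratio of 1.25, not a doubling) p = 0.50, and the interval runs from 11 points better to 30 worse.

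**4. POSAS.** The plan gives no SD, so results are in SD units. The 95% half-width is t × √(2/n):

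- 1.991 × √(2/40) = 0.45 SD at 40 per arm
- 1.997 × √(2/34) = 0.48 SD at 34 per arm

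Power to detect 0.5 SD is 60% at 40 per arm and 53% at 34. Within a joint it is 34% at 20 and 29% at 17. The problem is the same in kind but milder.

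**5. Window.** Section 9.e.ii says six months; sections 9.f and 10 say 90 days. Section 10 also speaks of following outcomes for at least three months, but this does not settle the matter, because the same section closes data collection at the 90-day visit. POSAS is scored once, 2-6 weeks after surgery, which lies inside either window.

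**The case against.** The best defence is that the no-worse phrases are narrative. Section 1.2 is background and section 2.1 is one general sentence. The listed objectives and endpoints only evaluate and record, and the descriptive statistics in section 12 serve them. No non-inferiority hypothesis is declared. This stands, and it is why the main remedy is to align the wording rather than redesign the trial. It does not remove the mismatch: section 2.1 is headed as the primary study objective, and nothing in the plan could substantiate its second half.

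A reader might be tempted to go further in four ways that the documents do not support.

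- *That the team intends to read non-significance as no-worse.* No section says so. The point is only that no other basis is given.
- *That a doubling would probably be missed whatever the rate.* The pooled powers at 25-30% contradict this. Such rates cannot be ruled out, because the superficial list includes skin irritation, erythema and prolonged drainage.
- *That the sample size is wrong.* It reproduces for closure time, and the trial was not sized for these outcomes.
- *That the complication rates would have no meaning at all.* Two of the three sections agree on 90 days, and section 9.e.ii can be read as describing routine care visits. The text still needs reconciling.

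**Conclusion.** The point holds as a mismatch between the stated purpose and the planned analysis. Sections 1.2 and 2.1 imply that nothing is lost on cosmesis or wound complications, and section 12 has neither a margin nor an interval rule that could show it. That conclusion depends on no assumed rate.

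Its practical size does depend on assumed rates. At control rates of 5-20% the pooled test has 4-41% power for a doubling with full retention and 3-34% after the plan's 15% loss. At 25-30% it has about 56-73% and 49-62%. Equal observed rates of 5-20% still leave an excess of about 12-18 points unexcluded at 40 per arm.

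The closure-time comparison and its sample size are not affected. The window conflict is a real but separate inconsistency that concerns complications and not POSAS.

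**What to change.** **1. Analysis and wording.**

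- In section 12, report the barbed-minus-traditional difference with a 95% confidence interval, by a standard method stratified by joint. Do this for any superficial complication, any deep complication, needle sticks and glove perforations, and the patient and observer POSAS scores separately.
- First align the superficial lists. Section 9.e.ii includes need for oral antibiotics; the table of collected peri- and post-operative variables leaves it out of the superficial group and lists antibiotic therapy separately.
- State that conclusions rest on the interval and that a non-significant result will not be read as no-worse. The two can disagree near the boundary: 17/40 v 8/40 gives Fisher p = 0.053 with a Newcombe interval of +2 to +41 points.
- Keep the planned tests and the adjusted regressions as supporting analyses.
- Reword sections 1.2 and 2.1 to match the descriptive secondary objectives and endpoints.

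Keeping the no-worse wording with a margin is not a practical alternative at this size. With truly equal rates of 5%, 10% or 20%, an illustrative 10-point margin would be met only 34%, 26% or 21% of the time at 40 per arm.

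**2. Window.** Reconcile section 9.e.ii with sections 9.f and 10, and count complications over the same window in every patient. The POSAS timing needs no change.

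**Cost.** Text changes and a few interval calculations, with no new patients. The safety and cosmesis conclusion becomes visibly weaker. If the team settles on the longer window, data collection per patient lengthens.

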### **2.2. SPECIFIC AIMS**

*To evaluate the closure time, wound cosmesis, and efficiency of barbed suture closure following revision total hip and total knee arthroplasty compared to traditional closure.*

#### *Primary Objective*

1. To compare surgical complexity of the closures based on closure time

#### *Secondary Objectives*

1. To evaluate the cost effectiveness of using bidirectional barbed suture compared with traditional sutures in revision knee and hip arthroplasty
2. To evaluate prevalence of complications (including needle sticks and glove perforations) of using barbed suture in revision total joint arthroplasty
3. To evaluate the cosmetic result of barbed versus traditional suture in revision total joint arthroplasty
4. To quantify the number of sutures used for each type of closure
5. To perform cost analysis to determine most cost-effective closure

### **2.3 ENDPOINTS**

#### *Primary Endpoint*

1. Measure the time needed to properly close the wound with each technique

#### *Secondary Endpoints*

1. Record all complications (including needle sticks and glove perforations) and infections related to the wound closure
2. Calculate the cost difference based on supplies, personnel, and OR time between each technique
3. Gather pictures of wound following closure to evaluate the cosmetic result of barbed versus traditional suture in revision total joint arthroplasty using the Patient and Observer Scar Assessment Scale (POSAS)
4. Calculate the number of suture used and length of incision for each technique

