### 4.1. INCLUSION CRITERIA

1. Patients  $\geq$  18 years of age

2. Surgical candidates undergoing revision total knee or total hip arthroplasty for one of the following indications second stage of two stage reimplantation for infection, mechanical loosening, instability, polyethylene wear, stiffness, or periprosthetic fracture

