**ii. FOLLOW-UP EVALUATION**

Patients will be assessed at the two to four standard of care post-operative visits up to six months. As part of standard of care, at each visit the patient will be evaluated for any complications including:

- a. superficial: skin irritation, erythema, suture spitting, cellulitis, superficial wound dehiscence, seroma, hematoma, prolonged wound drainage, need for oral antibiotics, post operatively
- b. Deep: periprosthetic infection, arthrotoomy failure, extensor mechanism failure
- c. Other non-closure associated complications

For research purposes only, a clinical image of the scar will be taken and stored in the patients' medical record. Patients will be asked to fill out the patient component of the Patient and Observer Scar Assessment Scale (POSAS), surgeons will complete the observer scale. The POSAS is a validated reliable scar assessment tool used for the evaluation of linear surgical scars taking into account both surgeons and patients' perceptions. This will occur at one of the standard of care post-op appointments between 2-6 weeks after surgery.

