**Perioperative Variables**

Closure Time Incision Length Number of sutures used will be counted and recorded Any needle sticks or glove perforations Dressing Type Preoperative Incision Clinical Image
Postoperative Variables
Superficial wound complications: Skin irritation, erythema, suture spitting, cellulitis, superficial wound dehiscence, seroma, hematoma, prolonged wound drainage Deep wound complications: periprosthetic infection, arthrotomy failure, extensor mechanism failure Other non-closure associated complications Revision procedures for infection Revision procedures for any reason Post-operative antibiotic therapy Use of chronic antibiotic suppression therapy Post-operative Clinical Image (research only) POSAS Wound Score (research only)

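### Secondary endpoint 1 ties infections, and on one reading all complications, to the wound closure without a criterion or masked judge, out of line with the rest of the plan

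*Combined protocol and SAP*

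**What the plan says.** Section 2.3, first secondary endpoint: "Record all complications (including needle sticks and glove perforations) and infections related to the wound closure". No section says what makes an event related, who decides, or whether that person is masked to the suture.

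Other parts of the plan are wider:

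- The matching objective in section 2.2 has no relatedness condition: "To evaluate prevalence of complications (including needle sticks and glove perforations) of using barbed suture in revision total joint arthroplasty".
- Section 9.e.ii states that "at each visit the patient will be evaluated for any complications including" a list of superficial types, a list of deep types (periprosthetic infection among them), and a third class, "Other non-closure associated complications".
- The table of peri- and post-operative variables in section 9.f repeats those types and adds revision for infection and "Revision procedures for any reason".
- Section 12 compares the arms "for the aforementioned baseline, perioperative and postoperative variables".
- Section 14 defines adverse events whether or not they are judged suture-related. The suspension rule in section 15 counts infections needing re-revision, and wound drainage, with no attribution step.

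Eligible patients include those having the "second stage of two stage reimplantation for infection" (section 4.1).

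**The concern.** Section 2.1 states the trial's purpose as faster closure without a price in cosmesis or wound complications. Secondary endpoint 1 carries the complication half of that claim. If an event enters the endpoint only after someone judges that the closure caused it, the result depends on the assessor as well as on the suture.

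That assessor probably knows the arm. The operating team sees the suture, study staff perform the randomization (section 3.2.2), the principal investigator alone reviews safety (section 15), and for the scar scale "surgeons will complete the observer scale". Section 1.1 says closure currently follows surgeon preference, so views on the two techniques may already be held.

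Infection after second-stage reimplantation is the most exposed case. It could be labelled a recurrence or a closure-related event, and the plan offers no rule to separate the two. Section 1.1 itself cites wound dehiscence as a risk factor for recurrent infection in this setting, so on the protocol's own reasoning the two labels can overlap.

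**Working it through.** **1. The plan's own figures.** There is no event rate or power calculation for complications. The closure-time sample size reproduces: with a 5-minute difference, SD 5 and one-sided alpha 0.025, the exact t-test power is 78.1% at 16 per group and 80.7% at 17. Then 34 / 0.85 = 40 per joint, and 2 × 40 = 80 in total. With equal groups this gives 80 / 2 = 40 per arm pooled and 40 / 2 = 20 per arm within one joint. These figures do not depend on the complication endpoint; they only set the arm sizes used below.

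**2. The passages side by side.**

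| Place | Is a judgement of cause needed? |
|---|---|
| 2.2, secondary objective 2 | No |
| 2.3, secondary endpoint 1 | Yes for infections; for other complications, on one reading |
| 9.e.ii, superficial and deep lists | No, listed by type |
| 9.e.ii, third class | Unclear: a residual class or a causal class |
| 9.f, variables table | No for the listed wound types and for revision for any reason; the third class recurs |
| 12, comparison by arm | None stated |
| 14, adverse event definition | No |
| 15, suspension rule | No |

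Section 2.3 stands apart. Its sentence can yield two endpoints, and nothing fixes the choice before data are seen.

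**3. How far attribution could move the result.** Every rate and share here is an assumption. Counted risk = true risk × share attributed to closure. The chance of significance is the sum, over all pairs of event counts, of the two binomial probabilities wherever the two-sided Fisher p is at most 0.05 (the test and level in section 12). Full recruitment and no losses are assumed.

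| True risk, barbed v conventional | Share attributed | Counted risk | Significant, 40 v 40: all events → counted | Significant, 20 v 20: all events → counted |
|---|---|---|---|---|
| 10% v 10% | 50% v 100% | 5% v 10% | 1.7% → 4.3% | 1.2% → 1.7% |
| 20% v 20% | 50% v 80% | 10% v 16% | 2.8% → 7.0% | 2.3% → 3.5% |
| 20% v 20% | 50% v 100% | 10% v 20% | 2.8% → 16.2% | 2.3% → 7.3% |
| 30% v 30% | 50% v 100% | 15% v 30% | 2.8% → 28.1% | 2.5% → 12.4% |
| 25% v 10% | 40% v 100% | 10% v 10% | 33.4% → 1.7% | 14.4% → 1.2% |
| 30% v 10% | 50% v 100% | 15% v 10% | 53.4% → 5.4% | 24.2% → 2.9% |
| 30% v 10% | 50% v 50% | 15% v 5% | 53.4% → 18.3% | 24.2% → 7.0% |

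The first four rows have equal true risks, so significance is a false positive; the next two have a true excess that uneven attribution removes. In the last row attribution is even-handed, and power still falls because fewer events are counted. With equal true risks and equal shares, the false-positive chance is not inflated.

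**The case against.** The strongest case against is that the plan applies no such filter in practice. The endpoint sentence opens by recording all complications, and the qualifier may attach only to infections. The follow-up section sorts events mainly by type, so cellulitis, dehiscence, drainage and periprosthetic infection already have a named place, and the third class reads naturally as a residual. Section 12 compares the collected postoperative variables by arm, so an attribution-free comparison is already planned.

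Much of this stands, and it rules out several stronger readings:

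- **That the endpoint is plainly limited to closure-caused events.** For complications other than infection this is only one reading.
- **That a recurrent infection after reimplantation goes uncounted.** No section says so; the plan is silent on how it is classed.
- **That the treating surgeons decide relatedness.** Surgeons are named as raters only for the scar scale. That the assessor knows the arm is a probable inference, not a stated fact.
- **That a harm would be hidden, or that the qualifier can only bias.** The events and all-cause revisions are recorded and compared, and a relatedness condition can also remove truly unrelated events.

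It is also fair that the illustrations use strongly uneven attribution, and that milder shares move the result less. Removing the qualifier would not cure unmasked detection and grading of subjective signs such as erythema.

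None of this settles which version is the declared endpoint. Section 2.3 names the qualified one, and no section makes the unqualified comparison the safety result.

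**Conclusion.** The point holds as a matter of definition. The declared safety endpoint carries an undefined relatedness condition, certain for infections and possible for all complications, which its own objective and the other safety sections lack. It could therefore differ from the by-type comparison in section 12, most plausibly for infection after second-stage reimplantation.

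The size of any bias cannot be known from the documents. On the assumed rates at 40 v 40, it runs from slight (1.7% to 4.3% false positives at a 10% risk) to large (53.4% to 5.4% power for 30% v 10%). These show direction and scale under strong attribution and are not forecasts. The conclusion does not need them: it rests on the wording and on the absence of a criterion and of masking. This is a modest but worthwhile correction to an unpowered secondary endpoint.

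**What to change.** Remove the relatedness qualifier from secondary endpoint 1. Define the endpoint as any superficial or deep wound complication listed in the section 9.f variables table, any infection of the operated joint, or any needle stick or glove perforation, from closure to the end of follow-up, counted by arm regardless of judged cause. State one end date for the count, since section 9.e.ii runs visits to six months while sections 9.f and 10 end at 90 days.

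Show judged relatedness only as a descriptive column. If a closure-related subset is also wanted, give its criteria and have it classified by someone masked to the arm.

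The main change is one sentence and needs no new event data. Its cost is that some unrelated events enter both arms and add a little noise. A masked classification, if chosen, would add some effort.
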